15.1.1. DERIVATIONS

Compliance with study medication will be calculated on the number of ampules count (total dispensed – total returned) divided by the prescribed number of ampules expressed as a percentage, see calculations below.

Patient should take the study medication twice daily and record it in their e-Diary apart from Week 24 visit when patient’s last dose will be in the morning.

Patients are dispensed ampules at Visit X and return at Visit X+1, however in the eCRF returned ampules will be recorded under Visit X.

- For time interval compliance to study medication will be calculated as follows:

$$\frac{([N \text{ of Ampules dispensed at Visit X}] - [N \text{ of Ampules returned at Visit Y}])}{\text{Denominator1}} * 100$$

Where Denominator1 is calculated with the following rules:

- N_1 = Number of ampules expected calculated based on total N of Ampules dispensed, taking into account 2 ampules per day, apart from last dose date for completed patients where we would only consider 1 ampule per day.
- For non-Week 24 return ampules visit: N_2 = Number of ampules between dispensing and returning visit calculated: $\{[Date \text{ of Visit Y}] - [Date \text{ of Dispensing at Visit X}] + 1\} * 2$.
- For Week 24 return ampules visit: N_2 = Number of ampules between dispensing and returning visit calculated: $\{[Date \text{ of Visit Y}] - [Date \text{ of Dispensing at Visit X}] + 1\} * 2 - 1$.

- If $N_1 \geq N_2$ then Denominator1 = N_2 .
- If $N_1 < N_2$ then Denominator1 = N_1 .
- Overall Compliance to study medication will be calculated as follows:

$$\frac{(\text{N of Ampules total dispensed} - \text{N of Ampules total returned})}{\text{Denominator2}} * 100$$

Where Denominator2 is calculated with the following rules:

- N_1 = Number of days calculated based on total N of Ampules dispensed, taking into account 2 ampules per day, apart from last dose date for completed patients where we would only consider 1 ampule per day.
- N_2 = Number of days between dispensing and returning visit calculated: $\{ \{ [\text{Date of Visit X(n)}] - [\text{Date of Dispensing at Visit 1}] + 1 \} * 2 \} - 1$.
- If $N_1 \geq N_2$ then Denominator2 = N_2 .
- If $N_1 < N_2$ then Denominator2 = N_1 .

For patients who permanently discontinue the study medication, the “Date of Visit X(n)”/ “Date of Visit Y” will be replaced by the last dose date of study medication, as specified in section 14 of the SAP. Whereas for patients who completed study, the “Date of Visit X(n)”/ “Date of Visit Y” will be replaced by date of last dose.

Drug intake as recorded in the e-diary: percent of ‘yes’ responses. The denominator is the number of records for which the patient provided an answer (Yes or No) to drug intake questions (morning and evening) in the e-diary.

For time interval study medication e-diary compliance, use week’s windowing conventions described in section 6.4 of the SAP. Use study day assigned to determine the date for weeks required or the time intervals, Week 12 and Week 24. The compliance will be calculated as follows:

$$\frac{(\text{Week X}^* < \text{number of 'yes' responses entered in the eDiary} \leq \text{Week Y})}{(\text{Week X}^* < \text{number of non - missing responses entered in the e - Diary} \leq \text{Week Y})} * 100$$

*If Week X = Day 1, update “<” to be “≤”. If Week Y is Week 24 and patient has completed treatment then the last entry we expect in the morning. Patient should not log any entries from and including evening of Week 24.

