8.6.1 Site-Level Disaster Plan

It is recommended that investigative sites prepare a written Disaster Plan for this study which describes how the site will manage patient activities and procedures in the event that site is not operating normally, site equipment is not available, and/or patient(s) cannot attend an in-clinic study visit. This written Disaster Plan could include but not be limited to a description of how the following activities and procedures will be conducted for remote visits or phone/video contact:

- Phlebotomy collection
- Vital signs collection
- Blinded study medication distribution
- Rescue albuterol/salbutamol distribution

8.6.2 **Unscheduled Visit**

8.6.2.1 ***Blinded Study Medication and/or Rescue Medication***

If blinded study medication and/or rescue albuterol/salbutamol cannot be dispensed at a scheduled clinic visit or if a patient will likely run out before attending a scheduled clinic visit, the medication may be dispense alternatively in line with according to local requirements.

Blinded study medication and/or rescue medication can be collected, and compliance can be assessed at the next in-clinic visit.

8.6.2.2 ***Study Supplied Nebulizer Replacement***

If a study supplied nebulizer cannot be distributed at a scheduled clinic visit or if the study supplied nebulizer requires replacement before attending a scheduled clinic visit, the study supplied nebulizer may either be picked-up by the patient directly outside the clinic, sent to the patient's home via trackable mail/postal service (unless restricted by local requirements), or given to the patient at the next scheduled visit.

8.6.2.3 ***Other Contingencies***

- eDiary: In the event of a problem with the eDiary or the paper diary for recording of medications and information specific to the PK procedures and sample analysis, a replacement eDiary and/or paper diary may either be picked-up by the patient directly outside the clinic or sent to the patients home according to local requirements.
- Rescue medication (albuterol/salbutamol): In the event that albuterol/salbutamol is in short supply/not available in a given country or region, another medication may be substituted following consultation and approval by the Medical Monitor (unless restricted by local requirements).

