14. STUDY MEDICATION EXPOSURE

Exposure to study medication in days will be presented for the SAF set.

The dates of first dose of study medication administration will be taken from the “Drug Exposure” page of the eCRF (Day 1). The date of last dose of study medication administration will be taken as the latest date among all from the “Drug Exposure” and “Drug Exposure – Evening Blinded Study Medication Clinic Dosing” pages of the eCRF.

If no drug exposure were made at last visit and the dispensed drug supply was insufficient to cover use up to last visit, the last exposure day will be set to the day the drug supply should have been empty if patient had been compliant to twice daily regimen.

Interruptions and compliance are not taken into account for duration of exposure.

Study medication exposure will be presented using summary statistics by total number of days, and using frequency counts by subgroups: 1-42 days, 43-84 days, 85-126 days, 127-168 days and >168 days.

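### SAP 15.1.1 caps the ampule-compliance denominator at the ampules dispensed, so a supply gap of about 23 to 29 days or more before Week 12 can escape the non-compliance flag

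*SAP*

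**What the plan says.** SAP Section 15.1.1 describes compliance as ampules dispensed minus ampules returned, "divided by the prescribed number of ampules expressed as a percentage". The detailed rules then define two candidate denominators.

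- **N1 (interval):** "Number of ampules expected calculated based on total N of Ampules dispensed, taking into account 2 ampules per day", with one ampule on the last dose date for completers.
- **N2 (interval):** "Number of ampules between dispensing and returning visit calculated" as twice the inclusive days, minus 1 when the return visit is Week 24.
- **Choice:** the smaller is used. The operative line is "If $N_1 < N_2$ then Denominator1 = N_1", and overall compliance (Denominator2) has a parallel rule. There N1 is a "Number of days calculated based on total N of Ampules dispensed, taking into account 2 ampules per day", while the N2 formula doubles the days and subtracts 1.

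SAP 15.1 flags non-compliance from the ampule count alone: 70% or less from Day 1 to Week 12, or 50% or less over the study. Time after treatment withdrawal is left out.

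Short supply is foreseen. Protocol 8.6.2.1 provides for alternative dispensing "if a patient will likely run out before attending a scheduled clinic visit". SAP 14 has a rule for when there was no dosing at the last visit and "the dispensed drug supply was insufficient to cover use up to last visit".

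SAP 5.7 excludes from the per-protocol set patients who stopped study medication before Day 74. Other exclusions are settled at the blinded data review, and non-compliance is one possible reason.

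**The concern.** The stated principle is compliance against prescription; the rule that would be programmed is compliance against supply. Because the smaller of N1 and N2 is always at most N2, the cap can raise the figure but never lower it. When supply falls short of the interval, the doses the patient never had drop out of the denominator.

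The cap is not needed to remove off-treatment time. SAP 15.1 and 15.1.1 already do that by ending the calculation at the last dose date.

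Two things are at stake. The compliance tables in SAP 15 would place some patients in too high a class. And the Week 12 flag, which the blinded data review may consult when settling the per-protocol set, could miss patients with a long break before the Week 12 spirometry.

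The overall measure has a separate fault: one of its two candidate denominators is described in days, while the formula for the other yields ampules.

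**Working it through.** The plan gives no worked compliance value to reproduce, so the check applies the SAP 15.1.1 formulas directly.

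**Inputs.** Two ampules per day, N1, N2 and the cap (SAP 15.1.1); cut-offs of 70% and 50% (SAP 15.1); visit window of ±10 days (SAP 6.4). Kit size is not in the documents, so ampule numbers per dispensing are assumptions.

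**Formulas.** SAP figure = 100 × (dispensed − returned) / min(N1, N2). Against prescription = 100 × (dispensed − returned) / N2.

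**1. Gap before Week 12, Week 12 on Day 85, nothing returned, drug resumed.** N2 = (85 − 1 + 1) × 2 = 170. With g days lacking drug, 170 − 2g ampules are dispensed and used.

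| Days without drug | Used / N2 | Against prescription | SAP figure |
|---|---|---|---|
| 14 | 142/170 | 83.5% | 100% |
| 21 | 128/170 | 75.3% | 100% |
| 25 | 120/170 | 70.6% | 100% |
| 26 | 118/170 | 69.4% | 100% |
| 28 | 114/170 | 67.1% | 100% |
| 42 | 86/170 | 50.6% | 100% |

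**2. Shortest gap that changes the Week 12 flag.** (2D − 2g)/(2D) ≤ 0.70 requires g ≥ 0.3D. Day 75 gives 22.5, so 23 days; Day 85 gives 25.5, so 26; Day 95 gives 28.5, so 29. For the 50% full-study flag with Week 24 on Day 169, N2 = 169 × 2 − 1 = 337, and (337 − 2g)/337 ≤ 0.50 requires g ≥ 84.25, so 85 days.

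**3. Missed Week 6 resupply (assumed 84 to 104 ampules on Day 1, all used, Week 12 on Day 85).** Against prescription: 84/170 = 49.4% to 104/170 = 61.2%. SAP figure: 84/84 or 104/104 = 100%.

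**4. Some ampules returned.** With 114 dispensed and 23 returned by Day 85, use is 91. Against prescription: 91/170 = 53.5%, flagged. SAP figure: 91/114 = 79.8%, not flagged. The masking does not depend on zero returns.

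**5. Where the cap changes no flag.** Assume 84 ampules at both Day 1 and Week 6. The worst in-window timing is Week 6 on Day 33 and Week 12 on Day 95, with use 64 + 84 = 148. The SAP figure is 148/168 = 88.1%, against 148/190 = 77.9% of prescription; neither is flagged. With 100 per dispensing, 200 exceeds 190 and the cap does not bind.

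**6. Supply exhausted and never resumed (assumed 84 ampules).** Where the SAP 14 rule applies, last exposure is Day 42, so N2 = 84 and compliance is 84/84 = 100% with or without the cap.

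**7. Denominator2 read literally.** N2 = 337. With 337 ampules dispensed, N1 in days is 169 (168 days of two, plus one). A full complier scores 337/169 = 199%. A patient taking 90 of 337 doses (26.7%) scores 90/169 = 53.3% and passes the 50% cut.

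**The case against.** The strongest reply is that little follows from the cap. Several parts of it stand.

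- A reader might infer that a patient who runs out of drug therefore stays in the per-protocol set. The documents do not say so. SAP 5.7 does not import the SAP 15.1 cut-offs, and exclusions are decided at the blinded data review. That review could also draw on the regimen departures that Protocol 6.6 requires in the eCRF, or on diary answers.
- A reader might infer that any gap of some weeks is hidden from the flag. It is not: with nothing returned, up to 25 days on a Day 85 schedule stays above 70% under either denominator. A changed flag needs a missed or late resupply, or kits well short of the interval, and Protocol 8.6.2.1 exists to prevent that.
- If drug is never resumed, the SAP 14 rule can give 100% under either denominator. If the case is treated as discontinuation before Day 74, SAP 5.7 already excludes the patient.
- N2 alone is slightly too large outside Week 24, because it counts both doses on the return day. Day 1 to Day 43 gives 86, while Days 1 to 42 hold 84; 84/86 = 97.7% for a full complier. The cap happens to correct this.
- The unit fault in Denominator2 looks like a labelling slip. Programming checks should catch a 199% result.

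The e-diary measure is only a partial safeguard. "The denominator is the number of records for which the patient provided an answer (Yes or No) to drug intake questions", so a No lowers it but a blank entry drops out. The separate diary-completion figure in SAP 15.2.1 falls when days are missing, but neither measure enters the SAP 15.1 flag.

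These points limit how often the rule matters. They do not reconcile it with the SAP's own reference to prescribed ampules.

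**Conclusion.** The point holds in a limited form. For a patient who runs short and later resumes, SAP 15.1.1 gives a compliance value that contradicts its own stated basis. With nothing returned, the value is 100% however long the gap. The Week 12 flag is wrong once the gap reaches about 23 to 29 days (26 with Week 12 on Day 85); the full-study flag needs about 85 days. The tables are overstated for shorter gaps as well: the 49.4% example belongs in the lowest class of SAP 15 (below 50%) but would be reported at 100%.

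The 84 to 104 ampule example rests on an assumed kit size and a completely missed Week 6 resupply. The documents give no basis for saying how many patients would be affected.

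It would be wrong to infer that the main efficacy result is at risk. The primary analysis uses the mITT population under a treatment-policy strategy (SAP 2.5 and 16.1), and the per-protocol analysis is a sensitivity analysis. What is affected is the compliance reporting and one input that the blinded data review may use.

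**What to change.** In SAP 15.1.1:

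- Set Denominator1 and Denominator2 to N2, the prescribed doses from dispensing to the return visit or last dose, and delete the rules that substitute N1 when it is smaller.
- For intervals not ending at Week 24, leave out return-day doses that come from the next supply, so that a full complier is not scored below 100%. This does not move the Week 12 thresholds: with the whole return day removed, g ≥ 0.3(D − 1) gives 22.2, 25.2 and 28.2, again 23, 26 and 29 days.
- State N2 of Denominator2 in ampules. If a supply-adjusted figure is wanted, keep N1 (also in ampules) for a labelled secondary display that does not drive the non-compliance flag.

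The cost is SAP wording and programming, with no new data collection. The downside is that some patients with supply gaps will show lower compliance and may be considered for exclusion from the per-protocol set.

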15.1. STUDY MEDICATION COMPLIANCE

Study medication compliance will be summarized by treatment group in 2 ways:

- The number of ampules dispensed and unused returned will be taken from “Drug Accountability” page of the eCRF.
- Drug intake as recorded in the e-diary.

Patient is non-compliant, for study medication intake collected through the number of ampules dispensed/returned, if identified as taking less than or equal to 70% of blinded study medication during the period Day 1 to Week 12, or less than or equal to 50% over the study (Day 1 to Week 24). Calculations will not include time after treatment withdrawal.

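### The overall ampule-compliance denominator in SAP 15.1.1 mixes days with ampules; followed as written, it inflates full-study compliance about 1.7 to 2 times for completers supplied close to need

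*SAP*

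**What the plan says.** SAP 15.1.1 states the principle first: compliance is ampules dispensed minus ampules returned, "divided by the prescribed number of ampules expressed as a percentage". Two calculations follow.

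- **Interval compliance (Denominator1).** N1 is the "Number of ampules expected calculated based on total N of Ampules dispensed, taking into account 2 ampules per day". N2 is the "Number of ampules between dispensing and returning visit calculated", with a formula of twice the inclusive days, less one when the return visit is Week 24. Both are in ampules, and the smaller one is used.
- **Overall compliance (Denominator2).** N1 is the "Number of days calculated based on total N of Ampules dispensed, taking into account 2 ampules per day", with one ampule on the last dose date for completers; no formula is given. N2 is the "Number of days between dispensing and returning visit calculated", but its formula is the inclusive days since first dispensing, times 2, minus 1. If N1 is at least N2, "then Denominator2 = N_2"; otherwise N1 is used.

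The end date is the last dose, both for completers and for patients who stop study medication.

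SAP 15 requires full-study compliance to be summarized, including frequency bands that end in one above 100%. SAP 15.1 calls a patient non-compliant at 70% or less from Day 1 to Week 12, "or less than or equal to 50% over the study (Day 1 to Week 24".

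**The concern.** In the overall calculation the numerator is in ampules, N2 is computed in ampules, and N1 is described in days. A minimum taken over two different units has no meaning, and at two ampules a day the days figure is usually the smaller. A program that follows the text would then divide ampules by days.

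Two outputs are at stake. In the full-study compliance table, adherent completers would land in the above-100% band. The overall non-compliance flag would miss patients who took well under half of their doses. Because N1 has no formula, two programmers could each defend their reading and differ by up to a factor of two.

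**Working it through.** The documents give no numerical compliance result, so there is no figure to reproduce. The check applies the stated rule.

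**Inputs**
- d = inclusive days from first dispensing to last dose. For a completer d = 169, the upper end of Week 24 in SAP 6.4.
- D = total ampules dispensed. The documents do not give it. For completers 340 to 400 is assumed.
- Dispensing at Day 1, Week 6 and Week 12 (Protocol 1.3). For patients who stop, 84, 84 and 168 ampules are assumed at these visits, with no spare.

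**Formulas**
- N2 = 2d − 1.
- N1 read as written, in days: D/2, or (D + 1)/2 for a completer, whose last day needs one ampule.
- Denominator2 = the smaller of N1 and N2.
- Inflation = min(D, N2) / min(N1, N2), that is, the denominator with both terms in ampules over the literal one.

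**Completers.** N2 = 2 × 169 − 1 = 337 prescribed ampules.

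| D (assumed) | N1, days | All 337 used | Half used (168.5) | True intake that reads 50% |
|---|---|---|---|---|
| 340 | 170.5 | 337/170.5 = 197.7% | 98.8% | 0.5 × 170.5/337 = 25.3% |
| 360 | 180.5 | 186.7% | 93.4% | 26.8% |
| 400 | 200.5 | 168.1% | 84.0% | 29.7% |

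More spare supply lowers the inflation: 420 ampules gives 160.1% at full intake.

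**Patients who stop.** N2 runs only to the last dose, while N1 uses everything dispensed. The days figure is chosen only if D/2 < 2d − 1, that is D < 4d − 2.

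| Last dose | D | N1, days | N2, ampules | Smaller | Inflation |
|---|---|---|---|---|---|
| Day 21 | 84 | 42 | 41 | N2 | 1.00 |
| Day 30 | 84 | 42 | 59 | N1 | 1.40 |
| Day 42 | 84 | 42 | 83 | N1 | 1.98 |
| Day 43 | 168 | 84 | 85 | N1 | 1.01 |
| Day 85 | 336 | 168 | 169 | N1 | 1.01 |
| Day 120 | 336 | 168 | 239 | N1 | 1.42 |
| Day 160 | 336 | 168 | 319 | N1 | 1.90 |

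With 20 spare ampules at each dispensing, N2 is chosen, and the result is right, for last doses on Days 1–26, 43–52 and 85–99. The inflation therefore depends on stopping date and supply, and no single factor would correct it afterwards.

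**With N1 in ampules.** For the same completer the denominator is 337 at each of these supplies. Full use gives 337/337 = 100%; half use gives 168.5/337 = 50%, which meets the limit.

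**The case against.** The strongest reply is that days is only a wrong label. The governing sentence speaks of prescribed ampules. N2 bears the same label over a formula that plainly counts ampules. The rest of N1's description, including the single ampule on a completer's last day, matches the interval version, where N1 is in ampules. Nothing in the text tells the programmer to divide by 2. On that reading there is no inflation. This is plausible and may be what was intended, but it cannot be confirmed: N1 has no formula, and a number of days worked out from ampules at two per day reads naturally as a division.

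The impact is also limited, and these points stand:
- The 70% criterion for Day 1 to Week 12 is an interval measure and uses the sound denominator.
- Diary compliance is computed separately.
- The primary analysis is on the mITT population under a treatment-policy strategy, and compliance is not a model term.
- SAP 5.7 lists non-compliance as a possible reason for per-protocol exclusion, but it ties exclusions to lung function at Week 12 and does not name a compliance measure.

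A reader might infer that the rule always selects the days figure and nearly doubles every patient's compliance. It does not: when D is at least 4d − 2, as for some early stoppers, N2 is selected and the result is correct. Nor does the 50% limit become useless; it would still flag very low intake.

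**Conclusion.** The definition is wrong as written, with limited consequences. Read literally, it inflates overall compliance by about 1.7 to 2 times for completers and others supplied close to need, and by 1.0 to 2.0 times for patients who stop, depending on when. A completer would meet the overall non-compliance rule only at a true intake of about 25% to 30%. These sizes rest on 169 days of treatment, on the assumed supplies, and on reading N1 as days; if N1 was meant in ampules the inflation is nil.

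The exposed outputs are the full-study ampule-compliance summary and the overall non-compliance flag. A reader might also infer that the per-protocol population is compromised. That is possible, because the flag could be used at the blinded data review, but the documents do not say that it is.

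**What to change.** In Denominator2, define N1 as the number of ampules expected from the total dispensed, with an explicit formula in ampules that shows how the last-day adjustment for completers enters. Relabel N2 as the number of ampules prescribed from first dispensing to last dose; its formula can stay. Both then match Denominator1. Check the compliance program against the revised text and, if it used days, rerun the full-study ampule summary and the overall flag.

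The cost is two definitions in the SAP and a program check. No data collection, design element or efficacy model changes.

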15. COMPLIANCE

Compliance to study medication based on dispensed and returned unused ampules and secondarily based on e-Diary entries will be presented for the SAF set.

Compliance will be presented using summary statistics by time intervals (Day 1 to Week12, Weeks 12-24 and full study length), as well as using frequency counts by subgroups: <50%, 50-70%, 70-80%, 80-90%, 90-100% and >100%.

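### The last-dose-date substitution in SAP 15.1.1 is not limited to the interval in which dosing ends, so Day 1 to Week 12 compliance can be divided by ampules supplied instead of ampules due

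*SAP*

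**What the plan says.** SAP 15 reports compliance "by time intervals (Day 1 to Week12, Weeks 12-24 and full study length". SAP 15.1 calls a patient non-compliant on ampule counts for "taking less than or equal to 70% of blinded study medication during the period Day 1 to Week 12", or at 50% or less over the whole study.

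SAP 15.1.1 introduces the interval calculation with "For time interval compliance to study medication will be calculated as follows". The numerator is ampules dispensed minus ampules returned. Denominator1 is the smaller of two terms:

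- N1, the supply term: "Number of ampules expected calculated based on total N of Ampules dispensed, taking into account 2 ampules per day".
- N2, the calendar term, described as the ampules falling between the dispensing and the return visit. The line beginning "For non-Week 24 return ampules visit" sets it to (Date of Visit Y − date of dispensing + 1) × 2. A separate line for the Week 24 return subtracts one.

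The closing paragraph on ampule counts then changes the end date. For patients who permanently discontinue drug, Date of Visit X(n) and Date of Visit Y "will be replaced by the last dose date of study medication, as specified in section 14 of the SAP". For patients who completed the study they "will be replaced by date of last dose". SAP 14 gives each patient one such date: "The date of last dose of study medication administration will be taken as the latest date among all" the dosing pages of the eCRF.

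SAP 5.7 lists non-compliance among the reasons that may lead to exclusion from the per-protocol population, to be specified at a blinded data review meeting.

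**The concern.** Substituting the last-dose date is sensible for the interval in which dosing stops. It is wrong for an interval that has already closed. Completers and permanent discontinuers together cover essentially all treated patients, and neither sentence exempts an interval. Followed as written, the actual return-visit date would almost never be used, and the Day 1 to Week 12 interval of a completer would run to the Week 24 dose. That conflicts with the same section's description of N2 and with its stated aim of dividing by the ampules prescribed.

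The affected interval carries the 70% cut. The per-protocol set, built around lung function at Week 12, is used for sensitivity analyses of the primary endpoint (SAP 16.1.4) and the key secondary endpoints (SAP 16.2.4). A biased count could change who is considered for exclusion, and would distort the Day 1 to Week 12 compliance tables.

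**Working it through.** The SAP gives no worked compliance figure to reproduce, so this applies its formula directly.

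**Inputs**

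- On-schedule completer: Day 1 dispensing, Week 12 visit on Day 85, last dose on Day 169.
- Drug is dispensed at Visits 1 and 2 before Week 12 (Protocol 1.3). The check pools both, although the SAP formula names a single dispensing visit.
- Full use by Week 12 is 84 × 2 = 168 ampules.
- Ampules dispensed by Week 12 (N1, taken per interval): not in the documents. **Assumed range** 172 to 240.

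**Calendar term**

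- End date at the return visit: N2 = (85 − 1 + 1) × 2 = 170.
- End date at the last dose, as written: N2 = (169 − 1 + 1) × 2 = 338.

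With N2 = 338, Denominator1 = min(N1, 338), which equals N1 for any supply below 338.

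**Effect on the reading**

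Reading at full adherence = 168 / Denominator1. True adherence that reads as 70% = 0.70 × Denominator1 / 168.

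| Case | Denominator1 | Full adherence reads | True adherence reading as 70% |
|---|---|---|---|
| Return-visit date kept | 170 | 98.8% | 70.8% |
| As written, N1 = 172 | 172 | 97.7% | 71.7% |
| As written, N1 = 180 | 180 | 93.3% | 75.0% |
| As written, N1 = 208 | 208 | 80.8% | 86.7% |
| As written, N1 = 224 | 224 | 75.0% | 93.3% |
| As written, N1 = 240 | 240 | 70.0% | 100% |

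Example at 208 ampules: a patient with 85% true adherence uses 0.85 × 168 = 142.8. The reading is 142.8/208 = 68.7% (non-compliant), against 142.8/170 = 84.0% with the return-visit date.

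**Sensitivity**

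- Counting 170 ampules as full use moves the 240 threshold to 243 (170/0.70 = 242.9).
- An early Week 12 visit lowers it. On Day 75, the edge of the ±10-day window, full use on that count is 150, and 150/0.70 = 214.3, so 215 ampules suffice.
- As an illustration only, supply covering the widest windows would be 53 × 2 = 106 (Day 1 to Day 53) plus (95 − 33 + 1) × 2 = 126 (Day 33 to Day 95), or 232. An on-schedule, fully adherent patient would then read 168/232 = 72.4%. The documents do not say that supply was sized this way.
- If N1 were programmed as the whole-study total (at least 338), Denominator1 = 338 and full adherence reads 168/338 = 49.7%.
- A patient who stops drug after Week 12 has N2 run to the stop date. For a stop on Day 120, N2 = 120 × 2 = 240.

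**Intervals not harmed**

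For Weeks 12–24, the last-dose date gives (169 − 85 + 1) × 2 − 1 = 169. For the full study it gives (169 − 1 + 1) × 2 − 1 = 337. Both are appropriate.

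**The case against.** The best defence is that only the final interval was meant. A separate line for returns before Week 24 would have no purpose if the return date were always overwritten. N2 is described in terms of the return visit, and the substitution names Date of Visit Y alongside the end date of the overall formula. This is a fair reading of the intent, and the paragraph is probably a drafting slip. It does not remove the point: the sentence as it stands gives a programmer an instruction that yields the wrong figure.

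The second objection, that the size rests on supply figures absent from the documents, stands in full. With 172 ampules the reading falls by about one point, and at 180 only true adherence between roughly 71% and 75% changes class.

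A reader might infer three stronger things that the documents do not support:

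- **Every completer would read about 50%.** This needs N1 to be the whole-study total, or the supply cap to be absent. The SAP has the cap. Its wording on total ampules dispensed leaves the whole-study reading open but does not require it.
- **Misclassified patients drop out of the per-protocol set automatically.** SAP 5.7 says the reasons may include non-compliance and are specified at the blinded review. SAP 1 leaves the decision process to a separate plan, which is not available here.
- **The primary result is at risk.** The primary and secondary analyses use the mITT population, which does not depend on compliance.

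**Conclusion.** The rule is wrong as written and should be corrected. For completers it makes the Day 1 to Week 12 denominator the ampules supplied, so the effective cut on true adherence rises from about 71% to somewhere between 72% and 93% for 172 to 224 ampules dispensed. A fully adherent patient seen on schedule is misclassed only from about 240 ampules, or under the whole-study reading of N1. These figures rest on the assumed supply, Visit 1 and Visit 2 dispensing pooled, and a Day 85 visit.

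The consequence is limited to the Day 1 to Week 12 ampule-count tables and to which patients are put forward for possible per-protocol exclusion. The Weeks 12–24 and full-study figures are not affected by this substitution, nor is e-diary compliance, which has its own numerator and denominator. For patients who stop before Week 12 the substitution is suitable, because that interval contains their last dose.

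**What to change.** Replace the substitution paragraph in SAP 15.1.1 with a rule along these lines:

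- The end date of an interval is the earlier of the return-visit date and the last-dose date. The last-dose date therefore applies only to the interval that contains the last dose; earlier intervals keep the actual return-visit date.
- For Day 1 to Week 12, the numerator is the ampules dispensed at Visits 1 and 2 minus those returned from both.
- N1 is computed from the ampules dispensed for that interval, not for the whole study.

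With this rule the on-schedule denominator is 170 whenever supply is at least 170. Full adherence then reads 98.8% (168/170) whatever the spare supply, and the cut stays at about 71% true adherence. The cost is two or three sentences and one programming condition. It should be settled before the blinded data review fixes the per-protocol set.
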